[name]

E-mail: [contact]

Chongqing, September 1, 2022

Title: How the habitats created by MRI can predict the IDH mutation status and prognosis of the patients with high-grade gliomas

1. Study direction

Prediction of IDH mutation status and prognosis of high-grade glioma patients based on multi-parametric MRI habitat imaging.

The multi-parametric MRI involved in this study scheme generally includes the following types in ideal state: conventional MRI sequences, Dynamic Susceptibility Weighted Contrast Enhanced Magnetic Resonance Imaging (DSC-MRI), Dynamic Contrast Enhanced Magnetic Resonance Imaging (DCE-MRI), Diffusion Weighted Magnetic Resonance Imaging (DWI), Vessel Size Imaging (VSI), or Magnetic Resonance Spectroscopy (MRS), and multiple combinations of indefinite items are carried out according to different research purposes.

2. Study background and objective

2.1 Background

High-grade glioma (HGG) is the most common primary brain tumor in the central nervous system. It has a highly malignant biological behavior, and is also a disease with complex initial mechanism and in constant dynamic change. Despite the emergence of multi-modal therapy such as immune and molecular targeting in recent years, the overall prognosis of HGG patients has not been significantly improved, and the median survival time has not been significantly improved. The high invasiveness and recurrence rate of HGG can be attributed in part to the significant tumor heterogeneity. Studies have shown that tumors are not homogenous individuals but uneven distribution of tumor cell subsets with different gene mutations or dominant clonal populations formed by tumor stem cells establishing differentiation levels. Genetic

variation among these tumor subclones causes them to compete with each other and change dynamically driven by environmental selection pressures based on local action, in a pattern similar to the occupation of specific habitats by different species in an ecosystem. These tumor cell clusters with the same ability of environmental selection and cell evolution are called habitats.

In terms of imaging, it is not difficult to find significant heterogeneity in the tumor based on differences in signals and enhancement modes. However, there are inevitably subjective differences between observers in the description of medical images such as enhancement, necrosis, edema, and tumor boundaries. Therefore, there is an urgent need for an accurate, objective, quantitative and spatial imaging method to express tumor heterogeneity. Habitat imaging technique is based on this need. Habitat imaging is an image segmentation concept and quantitative analysis technology based on differences in tumor pathology, blood perfusion, molecular characteristics, etc., which can combine various imaging methods to reveal the pathophysiological significance behind tumor imaging heterogeneity and the relationship between regional differences in the microenvironment that drive tumor evolution and adaptive strategies of tumor cells, to evaluate and monitor the temporal and spatial evolution of tumor habitat and predict potential genotypes and phenotypes. In addition, habitat imaging has been proved by many studies that the quantitative parameters obtained from habitat or the radiomics features extracted from habitat can be used as a robust biomarker for the prediction of overall survival, molecular mutation status and clinical treatment effect of patients.

Above all, we have sufficient and firm reasons to deem that habitat imaging based on multiparametric MRI is more conducive to reflect the potential biological information inside the tumor and realize individualized diagnosis and treatment.

2.2 Study objective

The purpose of this study was to construct tumor habitat by combining preoperative or postoperative multi-parametric MRI imaging, so as

- (1) to reveal the spatial and/or temporal heterogeneity within tumors;
- (2) to explore the value of habitat imaging in the classification and molecular typing of HGG;
- (3) to investigate the value of parameters quantitatively obtained from habitat in predicting the overall survival time and risk factors of HGG patients;
- (4) to investigate the differential and predictive ability of HGG local recurrence and

intracranial long-distance recurrence;
(5) to verify whether the habitat imaging analysis was more accurate than the traditional holistic tumor analysis in the above studies.

3. Study program

3.1 Study center

The study was a single-center observational retrospective study with data from the hospital information system. The subjects of the study were HGG patients who underwent MRI at the Army Medical Center of PLA (also known as Daping Hospital and the Research Institute of Surgery of the Third Military Medical University) from January 1, 2008 to December 31, 2021 (or at some interval within this period).

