3.2 Selection criteria

Inclusion Criteria (if we will predict the molecular status and overall survival):

- (1) the patient was over 18 years old;
- (2) the lesion was located in the supratentorial space;
- (3) a histopathologic diagnosis of HGGs according to the WHO CNS4/5;
- (4) all subjects were the first diagnosed cases without any invasive or non-invasive treatment;
- (5) access to the complete preoperative MR imaging examinations, at least including four conventional sequences.

Inclusion Criteria (if we will differentiate recurrence from distant intracranial recurrence):

- (1) the patient was over 18 years old;
- (2) the lesion was located in the supratentorial space;
- (3) a histopathologic diagnosis of HGGs according to the WHO CNS4/5;
- (4) underwent concurrent chemoradiotherapy with temozolomide after surgical resection or biopsy;
- (5) underwent preoperative and postoperative MRI, at least including four conventional sequences;
- (6) had newly appeared or enlarging, measurable, contrast-enhancing mass which raises clinical suspicion of tumor recurrence and distant intracranial recurrence;
- (7) adequate follow-up examinations to determine treatment response on clinic-radiological consensus or pathologic confirmation.

Exclusion Criteria:

- (1) patient with other brain tumors or other grade gliomas at the same time;
- (2) patient with severe basic diseases at the same time;
- (3) patient with a survival time of less than 30 days, which can be caused by severe surgical trauma stress;
- (4) poor image quality and heavy artifact affect the subsequent image processing.

4. Study data and variable collection

- (1) Basic clinical information:
age, sex, height, weight and previous underlying diseases of the patient;
- (2) Image and date collection:
the original MR image and the date of each MRI from preoperative to postoperative to recurrent to follow-up to the last examination, and records tumor location, volume, boundaries, and enhancement patterns;
- (3) Pathological and immunohistochemical data collection:
the specific diagnosis of high-grade glioma and specific molecular characteristics, including IDH, MGMT, TERT, 1p/19q, etc.
- (4) Methods of operation and postoperative treatment:
the extent of resection includes gross total resection, subtotal resection and partial resection, and the adjuvant therapy includes radiation, chemotherapy, chemoradiotherapy, untreated and unknown.
- (5) Prognostic data collection:

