specific overall survival time, recurrence time after treatment, whether there is an endpoint time.
- (6) Quantitative parameter collection:
the corresponding characteristic quantitative parameters were extracted according to different magnetic resonance sequences.

* The data will be collected from the Hospital Information System (HIS), Picture Archiving and Communication System (PACS) and telephone follow-up.

5. Advanced image processing and habitat construction

The multi-parametric MRI images of all patients will be exported from the PACS

system in DICOM format. First of all, all DICOM data will be converted to Nifti format. Subsequently, skull stripping will be performed. Next, the image will be resampled and registered. A deep learning model of nnU-Net will be employed to segment preliminary subregions of enhancing tumor, edema and necrosis on the four conventional structure sequences. Finally, the habitat construction will be carried out using a K-means clustering. Parameter values can be extracted quantitatively from habitats and radiomics features can be extracted quantitatively too.

6. Statistical analysis

Independent-samples T-test or Mann-Whiney U-test will be used to analyze the differences in quantitative parameter values between IDH-mutant HGGs and their wild-type counterpart in each habitat, using Benjamini-Hochberg's procedure for controlling the false discovery rate in multiple comparisons. The Chi-square testing will be used to analyze the constituent ratio of variables. ROC will be applied to evaluate the value of differentiating IDH mutation status and verify the differential efficacy of precise tumor habitats constructed by multi-parametric MRI and traditional tumor habitats. The cutoff values for each habitat were determined by using Youden index. The OS of HGG patients were analyzed using Kaplan-Meier survival analysis and Log-rank test. Specific statistical methods shall be formulated according to specific circumstances

7. Outcomes

Primary outcomes: multi-model habitats constructed by multiparametric MRI predict IDH mutation status and the prognosis in high-grade gliomas (in progress);

Secondary outcomes: multi-model habitats constructed by multiparametric MRI differentiate recurrence from distant intracranial recurrence (in the stage of preparation);

Exploratory outcomes: validate the advantages of habitat imaging and potential links to pathophysiology.

8. Ethical issues

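### Section 6 makes no use of the MRI dates that the plan collects, so calendar period could confound the pooled IDH comparison and, less plausibly, the survival comparison

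*Combined protocol and SAP*

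**What the plan says.** Section 3.1 describes the design: "The study was a single-center observational retrospective study with data from the hospital information system". Eligible scans run "from January 1, 2008 to December 31, 2021", with the qualifier "or at some interval within this period". The plan does not say which interval will be used.

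Section 4(2) records "the date of each MRI from preoperative to postoperative to recurrent to follow-up to the last examination", so calendar time is available for every patient.

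Section 6 uses t or Mann-Whitney tests with Benjamini-Hochberg control for habitat parameters by IDH status. It then says "ROC will be applied to evaluate the value of differentiating IDH mutation status", with a Youden cutoff for each habitat. For survival: "The OS of HGG patients were analyzed using Kaplan-Meier survival analysis and Log-rank test". Date, period, scanner and acquisition protocol do not appear as a stratum, covariate, split or sensitivity check. The section ends by leaving further methods to be settled as circumstances require.

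Two other passages bear on the point. Section 3.2 accepts "a histopathologic diagnosis of HGGs according to the WHO CNS4/5", which is two editions of the classification. Section 2.1 says, as general background, that the prognosis of these patients has not improved significantly.

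**The concern.** Pooling over calendar time is harmless if either the marker or the outcome is stable over time. If both move, period becomes a common cause. Suppose later scans give higher parameter values and later patients are more often IDH-mutant. The mutant group then contains more late scans, and a parameter with no relation to IDH within any period separates the groups in the pooled data. If the two trends run in opposite directions, a real signal is hidden. The same reasoning applies to survival.

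IDH status and prognosis together form the primary outcome in Section 7. The planned Benjamini-Hochberg step controls multiplicity and does nothing about confounding. Section 5 lists format conversion, skull stripping, resampling and registration, and states no intensity normalisation or harmonisation that might limit drift.

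**Working it through.** **Figures in the plan.** The window is 14.0 years at most. The documents give no sample size, IDH prevalence, event count or drift, so there is no stated figure to reproduce. Every input below is an assumption.

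**IDH, no true association.** Assume two equal periods, a normal parameter with SD 1, a mean shift *s* in the later period, and mutant share p₁ then p₂.

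- Late-period share among mutants: q_m = p₂/(p₁+p₂)
- Late-period share among wild-type: q_w = (1−p₂)/(2−p₁−p₂)
- Spurious mean difference: s(q_m − q_w)
- Pooled AUC: 0.5 + (q_m − q_w)[Φ(s/√2) − 0.5]

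For 10% then 20%: q_m = 0.20/0.30 = 0.667, q_w = 0.80/1.70 = 0.471, difference 0.196. With s = 0.5, Φ(0.354) = 0.638 and AUC = 0.5 + 0.196 × 0.138 = 0.527. With s = 1, Φ(0.707) = 0.760 and AUC = 0.5 + 0.196 × 0.260 = 0.551.

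For 5% then 20%: q_m = 0.20/0.25 = 0.800, q_w = 0.80/1.75 = 0.457, difference 0.343. The same steps give 0.547 and 0.589.

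Simulated two-sided 5% Mann-Whitney error for one parameter, N = 200:

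| Mutant share | Shift | Pooled AUC | Pooled error | Period-stratified error |
|---|---|---|---|---|
| 10% then 20% | 0.5 SD | 0.527 | about 7.5% | about 5% |
| 10% then 20% | 1 SD | 0.551 | about 14% | about 5% |
| 5% then 20% | 0.5 SD | 0.547 | about 12% | about 5% |
| 5% then 20% | 1 SD | 0.589 | about 30% | about 5% |

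Across repeated runs and a normal approximation, the pooled error spans about 7% to 31%. These rates precede the Benjamini-Hochberg step.

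**One link only.** With equal shares, q_m = q_w, so the AUC is 0.50 and the error 5% whatever the shift. With no shift, the result is the same whatever the shares.

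**Masking.** If the share falls from 20% to 10% while the parameter rises by 0.5 to 1 SD, a true within-period AUC of 0.75 reads 0.722 to 0.683 when pooled.

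**Survival, no true effect.** Assume exponential survival with an early-period median of 15 months, censoring uniform on 12 to 60 months, a median split of the parameter, N = 200 and 2,000 runs per setting.

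| Later/earlier HR | Shift | Pooled log-rank error | Stratified error |
|---|---|---|---|
| 0.8 | 0.5 SD | 6.7% | 5.4% |
| 0.8 | 1 SD | 8.7% | 5.0% |
| 0.67 | 0.5 SD | 6.5% | 4.0% |
| 0.67 | 1 SD | 14.5% | 5.2% |

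At HR 1 the pooled error is 4.8% to 5.4% at any shift, which is nominal within simulation error.

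**The case against.** The strongest reply is that the documents report no drift. They mention no scanner or protocol change, no trend in the IDH-mutant share and no survival by year. This stands, and it makes the whole point conditional. It does not remove the point, because nothing in the documents rules drift out and the date needed to check it is already collected.

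A reader might infer that the plan itself shows a changing period, from its variable MRI set ("multiple combinations of indefinite items are carried out according to different research purposes") or its list of adjuvant treatments. The text does not support that. The first concerns which sequences are used for which purpose, and the second is a list of data categories. Neither is tied to calendar time. Only the acceptance of two classification editions hints at change over time, and the documents do not say that it alters the mutant share or the parameter values.

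A reader might also infer that 14 years of scans will certainly be pooled. Section 3.1 allows a shorter interval, so 14 years is the upper limit. Since no interval is fixed, the exposure remains.

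The background statement in Section 2.1 weakens the survival route, because it runs against the assumed hazard ratios. It is not data from this centre, and a change in case mix or treatment mix could still link period to survival. The IDH route is untouched.

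The upper figures also need a mutant share that quadruples together with a full 1 SD shift. The milder settings give modest bias. Finally, the closing sentence of Section 6 permits later adjustment but commits to none.

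**Conclusion.** The omission is certain: the MRI date is collected and no stated analysis uses it. The bias is conditional on two simultaneous drifts that the documents do not report, and its size and direction are unknown. Under the assumed inputs the IDH comparison could move from a null AUC of 0.50 to between 0.527 and 0.589, with single-test error of about 7% to 31%. The survival comparison is a secondary concern, at about 6% to 15% error under the assumed hazard ratios. It would be wrong to read this as showing that the planned results are biased. The supported conclusion is that the plan cannot tell a habitat signal from a period effect if both drifts occur, and that a cheap safeguard is available.

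**What to change.** In Section 6:

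1. Fix the calendar interval, and the period cut-points for the preoperative MRI date, before habitats are linked to IDH status or survival.
2. Report habitat parameters, IDH-mutant share and OS by period, so that any drift is visible.
3. Beside the pooled analyses, pre-specify for IDH a period-stratified (van Elteren) rank test and an AUC computed over mutant/wild-type pairs from the same period, with a bootstrap interval. For OS, pre-specify a log-rank test stratified by period.
4. State that an association will be claimed only if it persists in the stratified analysis.

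This needs no new data. The cost is protocol wording, some extra analysis and slightly wider intervals, because cross-period pairs are not used. It is a partial remedy: stratified tests do not repair K-means labels or Youden cutoffs built on pooled data, and they do not address differences between scanners used in the same period.

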3.2 Selection criteria

Inclusion Criteria (if we will predict the molecular status and overall survival):

- (1) the patient was over 18 years old;
- (2) the lesion was located in the supratentorial space;
- (3) a histopathologic diagnosis of HGGs according to the WHO CNS4/5;
- (4) all subjects were the first diagnosed cases without any invasive or non-invasive treatment;
- (5) access to the complete preoperative MR imaging examinations, at least including four conventional sequences.

Inclusion Criteria (if we will differentiate recurrence from distant intracranial recurrence):

- (1) the patient was over 18 years old;
- (2) the lesion was located in the supratentorial space;
- (3) a histopathologic diagnosis of HGGs according to the WHO CNS4/5;
- (4) underwent concurrent chemoradiotherapy with temozolomide after surgical resection or biopsy;
- (5) underwent preoperative and postoperative MRI, at least including four conventional sequences;
- (6) had newly appeared or enlarging, measurable, contrast-enhancing mass which raises clinical suspicion of tumor recurrence and distant intracranial recurrence;
- (7) adequate follow-up examinations to determine treatment response on clinic-radiological consensus or pathologic confirmation.

Exclusion Criteria:

- (1) patient with other brain tumors or other grade gliomas at the same time;
- (2) patient with severe basic diseases at the same time;
- (3) patient with a survival time of less than 30 days, which can be caused by severe surgical trauma stress;
- (4) poor image quality and heavy artifact affect the subsequent image processing.

4. Study data and variable collection

- (1) Basic clinical information:
age, sex, height, weight and previous underlying diseases of the patient;
- (2) Image and date collection:
the original MR image and the date of each MRI from preoperative to postoperative to recurrent to follow-up to the last examination, and records tumor location, volume, boundaries, and enhancement patterns;
- (3) Pathological and immunohistochemical data collection:
the specific diagnosis of high-grade glioma and specific molecular characteristics, including IDH, MGMT, TERT, 1p/19q, etc.
- (4) Methods of operation and postoperative treatment:
the extent of resection includes gross total resection, subtotal resection and partial resection, and the adjuvant therapy includes radiation, chemotherapy, chemoradiotherapy, untreated and unknown.
- (5) Prognostic data collection:
specific overall survival time, recurrence time after treatment, whether there is an endpoint time.
- (6) Quantitative parameter collection:
the corresponding characteristic quantitative parameters were extracted according to different magnetic resonance sequences.

* The data will be collected from the Hospital Information System (HIS), Picture Archiving and Communication System (PACS) and telephone follow-up.

5. Advanced image processing and habitat construction

The multi-parametric MRI images of all patients will be exported from the PACS

system in DICOM format. First of all, all DICOM data will be converted to Nifti format. Subsequently, skull stripping will be performed. Next, the image will be resampled and registered. A deep learning model of nnU-Net will be employed to segment preliminary subregions of enhancing tumor, edema and necrosis on the four conventional structure sequences. Finally, the habitat construction will be carried out using a K-means clustering. Parameter values can be extracted quantitatively from habitats and radiomics features can be extracted quantitatively too.

6. Statistical analysis

Independent-samples T-test or Mann-Whiney U-test will be used to analyze the differences in quantitative parameter values between IDH-mutant HGGs and their wild-type counterpart in each habitat, using Benjamini-Hochberg's procedure for controlling the false discovery rate in multiple comparisons. The Chi-square testing will be used to analyze the constituent ratio of variables. ROC will be applied to evaluate the value of differentiating IDH mutation status and verify the differential efficacy of precise tumor habitats constructed by multi-parametric MRI and traditional tumor habitats. The cutoff values for each habitat were determined by using Youden index. The OS of HGG patients were analyzed using Kaplan-Meier survival analysis and Log-rank test. Specific statistical methods shall be formulated according to specific circumstances

7. Outcomes

Primary outcomes: multi-model habitats constructed by multiparametric MRI predict IDH mutation status and the prognosis in high-grade gliomas (in progress);

Secondary outcomes: multi-model habitats constructed by multiparametric MRI differentiate recurrence from distant intracranial recurrence (in the stage of preparation);

Exploratory outcomes: validate the advantages of habitat imaging and potential links to pathophysiology.

8. Ethical issues

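### Section 6 sets a Youden cutoff per habitat on the single study cohort and commits to no internal validation, so any sensitivity, specificity or J reported at those cutoffs for IDH status will be overstated on average.

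*Combined protocol and SAP*

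**What the plan says.** Section 3.1: "The study was a single-center observational retrospective study with data from the hospital information system". Patients are those scanned "from January 1, 2008 to December 31, 2021 (or at some interval within this period"). No section gives a number of patients, an IDH split or an expected AUC.

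Section 5 builds habitats by K-means and adds: "Parameter values can be extracted quantitatively from habitats and radiomics features can be extracted quantitatively too".

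Section 6 compares parameter values between IDH groups in each habitat, with Benjamini-Hochberg control. It then says that "ROC will be applied to evaluate the value of differentiating IDH mutation status" and that ROC will also compare multi-parametric habitats with traditional ones. Next comes "The cutoff values for each habitat were determined by using Youden index", followed directly by Kaplan-Meier and log-rank analysis of survival. The section closes with "Specific statistical methods shall be formulated according to specific circumstances".

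Section 7 gives the primary outcome as "multi-model habitats constructed by multiparametric MRI predict IDH mutation status and the prognosis in high-grade gliomas (in progress").

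No section mentions a training/test split, cross-validation, bootstrap or external cohort. Section 6 speaks of verifying efficacy, but that refers to comparing types of habitat. Section 7 speaks of validating advantages, but as an exploratory outcome. Neither is a validation of the cutoffs.

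**The concern.** The Youden cutoff is the value that maximises J = sensitivity + specificity - 1 in the patients at hand. Scoring the same patients at that value counts favourable chance variation as accuracy, so on average the result exceeds what the cutoff would deliver in new patients. Benjamini-Hochberg does not help, because it governs the group-difference tests and not the cutoff.

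IDH prediction is a primary outcome, and Section 2.1 presents habitat imaging as a way to "realize individualized diagnosis and treatment". Of the quantities that Section 6 could yield, accuracy at a cutoff is the closest to that aim and the one exposed to this bias.

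**Working it through.** The plan has no figure to reproduce, so the size was found by simulation with assumed inputs.

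**Inputs.** From the plan: one Youden cutoff per habitat, one cohort, no resampling. Assumed: one parameter, direction fixed in advance, true AUC 0.65/0.75/0.85, mutant share 15/25/40%, n = 60 to 600.

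**Model.** Parameter ~ N(d,1) in mutants and N(0,1) in wild-type, with d = √2 × z(AUC). For AUC 0.75, d = 1.414 × 0.6745 = 0.954. The best J that any cutoff can reach is 2Φ(d/2) - 1 = 2 × 0.6833 - 1 = 0.367. In each of 5000 replicates the empirical Youden cutoff was found. Apparent sensitivity, specificity and J were then compared with the population values at that same cutoff (delivered).

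**Central case (AUC 0.75, 25% mutant).** Excess J = apparent J - delivered J, e.g. 0.472 - 0.335 = 0.137.

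| n | Apparent J | Delivered J | Excess J | Excess sens. | Excess spec. | Samples with apparent > delivered |
|---|---|---|---|---|---|---|
| 60 | 0.472 | 0.335 | 0.137 | 0.105 | 0.032 | 90% |
| 100 | 0.447 | 0.343 | 0.104 | 0.077 | 0.026 | 88% |
| 200 | 0.420 | 0.350 | 0.070 | 0.052 | 0.018 | 86% |
| 400 | 0.402 | 0.356 | 0.046 | 0.034 | 0.011 | 84% |
| 600 | 0.394 | 0.358 | 0.036 | 0.027 | 0.009 | 82% |

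Mean apparent AUC was 0.750 at every n, so AUC is unbiased here.

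**Full grid.** Mean excess J was 0.102-0.188 (n=60), 0.077-0.145 (n=100), 0.050-0.099 (n=200), 0.034-0.068 (n=400) and 0.025-0.053 (n=600). The Monte Carlo SE is at most 0.0018.

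**Which group carries it.** At AUC 0.8 (mutant/wild-type):
- 20/80: sensitivity +0.084, specificity +0.020; 0.084/0.104 = 81% on the mutants.
- 75/25: sensitivity +0.023, specificity +0.073; 0.073/0.096 = 76% on the wild-type.
- 50/50: +0.040 on each.

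At 30/30 and AUC 0.75 it was +0.058 on each. The share of about 80% at 20/80 also held with mutant SD 0.6 and 1.5.

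**Remedies (central case, 1500 replicates).** Mean J, to be compared with the delivered J of this run:

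| n | Delivered | 10 × 5-fold CV | Bootstrap-corrected | One 70/30 hold-out |
|---|---|---|---|---|
| 60 | 0.334 | 0.335 | 0.388 | 0.327 |
| 100 | 0.343 | 0.338 | 0.377 | 0.336 |
| 200 | 0.350 | 0.348 | 0.371 | 0.344 |
| 400 | 0.356 | 0.355 | 0.369 | 0.353 |
| 600 | 0.358 | 0.358 | 0.369 | 0.356 |

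Cross-validation is close to unbiased. Bootstrap correction leaves 0.054 at n=60 and 0.011 at n=600. The hold-out is nearly unbiased but noisier: SD 0.236 against 0.150 for cross-validation at n=60. On root-mean-square error at n=60, bootstrap was slightly better than cross-validation (0.122 against 0.131 in one run, 0.143 against 0.154 in another). The level differs between runs but the order does not.

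**The case against.** The strongest reply is that the affected figures are not promised. No section says that sensitivity, specificity or J will be reported, and AUC, the ROC summary that needs no cutoff, is unbiased for a prespecified parameter. The cutoff sentence also stands between the ROC and survival sentences, so the cutoffs may be meant for IDH classification, survival grouping or both. This stands, and the point is therefore conditional on accuracy at the cutoff being reported for IDH status. It does not remove the point: the Youden index is itself computed from sensitivity and specificity, and the plan sets one cutoff per habitat.

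A second reply is that the size is not anchored in the documents and runs from 0.025 to 0.188. That is true, and it limits the claim to direction and an assumed range.

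A third is that Section 6 leaves methods open. It does, but permission to validate is not a commitment.

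A reader might infer more than the plan supports:
- **That the plan's IDH results, AUC included, are biased throughout.** AUC becomes optimistic only if habitats, parameters or features are selected or combined using IDH status. Section 6 neither states nor rules that out, and it was not simulated.
- **That sensitivity in particular is inflated.** This needs mutants to be the minority, and the IDH split is not given.
- **That an inflated cutoff will steer care.** The phrase on individualized care is a background remark on habitat imaging; no clinical use of a cutoff is proposed.

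**Conclusion.** The point holds in conditional form. The plan sets cutoffs on its only cohort and commits to no internal validation. Any sensitivity, specificity or J reported at them for IDH status would be too high on average, though not in every sample. Confidence is high on direction. The size rests wholly on assumptions (one binormal parameter, fixed direction, AUC 0.65-0.85, 15-40% mutant): mean J overstated by about 0.10-0.19 at n=60, falling to 0.03-0.05 at n=600. It should be fixed, but it can be fixed at analysis and does not undermine the design.

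**What to change.** State in Section 6 what the cutoffs are for. State also that any sensitivity, specificity and J reported at a Youden cutoff will be estimated by repeated stratified cross-validation. The cutoff, and any choice of habitat, parameter, direction, feature or model that uses IDH status, must be repeated inside each training fold. Report the results with 95% CIs, naming the interval method, beside the apparent values.

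Bootstrap optimism correction is an acceptable alternative if its residual optimism is stated. Apply the same procedure to AUC only where habitats, parameters or features are selected or combined using IDH status. Refitting K-means in each fold is optional: it uses no IDH labels, so it is not needed to remove cutoff optimism, and it would require a rule for matching habitats between folds.

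The cost is SAP wording and computing time, with no new patients or data. The downside is less favourable reported accuracy: in the assumed central case mean J falls by about 0.14 at n=60, 0.07 at n=200 and 0.04 at n=600.

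### Section 6 sets IDH cutoffs habitat by habitat and prespecifies no patient-level IDH score, and no rule for combining or choosing among habitats.

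*Combined protocol and SAP*

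**What the plan says.** Section 7 gives as the primary outcome that "multi-model habitats constructed by multiparametric MRI predict IDH mutation status and the prognosis in high-grade gliomas", and marks it as already in progress. Objective 5 in section 2.2 asks whether habitat analysis is more accurate than whole-tumour analysis.

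Section 5 builds the habitats: "Finally, the habitat construction will be carried out using a K-means clustering". The number of clusters is not stated. It adds: "Parameter values can be extracted quantitatively from habitats and radiomics features can be extracted quantitatively too". One habitat may therefore supply several candidate predictors.

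Section 6 gives the IDH analysis:

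- A t-test or Mann-Whitney test of "differences in quantitative parameter values between IDH-mutant HGGs and their wild-type counterpart in each habitat", with Benjamini-Hochberg control of the false discovery rate.
- "ROC will be applied to evaluate the value of differentiating IDH mutation status", and also to "verify the differential efficacy of precise tumor habitats constructed by multi-parametric MRI and traditional tumor habitats". The score that enters the curve is not defined.
- "The cutoff values for each habitat were determined by using Youden index".
- A closing provision: "Specific statistical methods shall be formulated according to specific circumstances".

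**The concern.** The primary outcome and objective 5 each need an accuracy figure for habitat imaging as a method. The stated analysis produces one figure per habitat, or more than one if several parameters are taken from each. Two problems follow.

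First, with a separate cutoff in each habitat, the same patient can fall on the mutant side in one and the wild-type side in another. The plan has no rule for that case, and the choice of rule changes sensitivity and specificity a great deal.

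Second, with several AUCs and no named lead, the natural course is to report the largest. That maximum is biased upward. If the whole-tumour comparator has one score and the habitat side has the best of several, the comparison in objective 5 leans towards habitats before any real difference is considered.

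**Working it through.** **No figure to reproduce.** The documents state no sample size, AUC, sensitivity, specificity, number of habitats or between-habitat correlation. The check has two parts: a reading of the text, and an illustration on assumed inputs.

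**Reading.** The methods named in section 6 are two-group tests with Benjamini-Hochberg, chi-square, ROC, the Youden index, Kaplan-Meier and log-rank. None combines habitats or parameters for one patient. Benjamini-Hochberg controls false discoveries across the group comparisons and does not combine predictors. No other section names a multivariable model, a classifier, a voting rule, or a lead habitat or parameter.

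**Assumed model.** There are K habitats, each with an equal-variance binormal marker of the same AUC and within-class correlation rho between habitats. Then:

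- Separation: d = √2 × z(AUC). For AUC 0.75, d = 1.414 × 0.6745 = 0.954.
- The Youden cutoff is the midpoint, so sensitivity = specificity = Φ(d/2) = Φ(0.477) = 0.68.
- P(calls conflict) = 1 − P(all positive) − P(all negative), by simulation for rho > 0.
- Best linear combination: d_c = d × √(K / (1 + (K − 1) × rho)), and AUC_c = Φ(d_c / √2).

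**Three habitats, AUC 0.75 each:**

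| rho | calls conflict | d_c | combined AUC | gain |
|---|---|---|---|---|
| 0.3 | 53% | 1.306 | 0.822 | 0.072 |
| 0.5 | 44% | 1.168 | 0.796 | 0.046 |
| 0.7 | 34% | 1.066 | 0.775 | 0.025 |
| 0.9 | 19% | 0.987 | 0.757 | 0.007 |

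At rho 0.7, 0.5 and 0.3, conflict is 22%, 29% and 35% with two habitats, and 41%, 53% and 63% with four.

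**Choice of rule.** With three habitats at rho 0.5, calling a patient mutant if any habitat is positive gives sensitivity 0.89 and specificity 0.45. Requiring all three gives 0.45 and 0.89. The difference, 0.89 − 0.45 = 0.44, is the conflict rate at rho 0.5.

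**Unequal habitats.** With AUCs 0.80, 0.70 and 0.70, the best linear combination has AUC 0.804, 0.800 and 0.802 at rho 0.5, 0.6 and 0.7. The gain over the best single habitat is at most 0.004.

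**Choosing the best habitat afterwards.** With three habitats of true AUC 0.75 and an assumed 20 mutants and 80 wild-type patients, the largest apparent AUC averages 0.78 to 0.79 (rho 0.7 down to 0.3). That overstates by 0.03 to 0.04 through selection alone.

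**Fitting error in a joint model.** With equal AUCs of 0.75, rho 0.7 and 20/80 patients, an unpenalised linear fit has an average true AUC of 0.759, and falls below 0.75 in about 20% of samples. At 15/60 the figures are 0.754 and about 29%. The AUC of a ridge-shrunken linear score, measured on the sample that fitted it, is too high by about 0.015 to 0.02.

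**The case against.** The strongest reply is that silence is not prohibition. A reader might infer that the plan cannot yield a single IDH prediction, or that joint information in the habitats will never be used. The documents do not support that. The closing sentence of section 6 leaves room for a joint model. The ROC sentence compares multi-parametric with traditional habitats and can be read as using a set-level score. What stands against this reply is that neither sentence defines a score, and the sentence after the ROC one sets cutoffs by habitat.

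Second, the primary outcome does not say that several habitats are pooled into one classifier. The multi-model wording may describe only how habitats are built from several sequences. In a retrospective, single-centre study, asking which habitat discriminates is legitimate, and no section proposes classifying patients from several simultaneous cutoffs. This is fair, and it is why conflicting calls are a possibility left open and not a stated procedure. It does not settle objective 5, which still needs a defined habitat score to set against whole-tumour analysis.

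Third, a reader might infer that the plan throws away discrimination by not combining habitats. That is not established. The gain needs habitats that are similarly informative and not too highly correlated. With unequal or highly correlated habitats it is close to nil, and fitting error in a small sample can absorb a modest gain. At correlation 0.3 to 0.5 with equal AUCs, the gain survives fitting. The case for one score therefore rests mainly on having a defined, unselected estimate, and less on a higher AUC.

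**Conclusion.** The point holds in this form: as written, the plan prespecifies no patient-level IDH score and no rule for combining or choosing among habitats, and its ROC comparison with traditional habitats has no defined habitat score. The supported claim is an absence of prespecification; it would go too far to say that a single prediction is ruled out.

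All sizes rest on assumed inputs. For three equally informative habitats at AUC 0.75, conflict runs from about 19% of patients (correlation 0.9) to 53% (0.3). The AUC gain from combining runs from about zero to about 0.07, the upper end being the favourable symmetric case. Best-of-three selection adds 0.03 to 0.04 to the apparent AUC at 20/80 patients. Conflict requires at least two habitats with informative cutoffs. The number of habitats is not given, but the wording implies more than one.

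The sponsor should make the change: it is cheap, and the primary outcome is already in progress.

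**What to change.** Make the primary IDH analysis one ridge or Firth logistic regression on a short list of habitat features fixed in advance. If there are too few mutants to support that, name one lead habitat and one parameter in advance instead; this also gives a single prediction.

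Report one predicted probability per patient and one AUC with a confidence interval, corrected for optimism by bootstrap or obtained by cross-validation, with all fitting steps repeated in each resample. If a cutoff is wanted, set one on that score. Use the same score as the habitat side of the comparison with traditional analysis. Keep the per-habitat ROC curves and Youden cutoffs as descriptive results.

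The cost is SAP wording and a little more analysis, with no new data. The coefficients will be estimated from few mutants, which the penalty and short list limit but do not remove. The reported AUC may be slightly lower than the best apparent single-habitat AUC.
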